**1. PROJECT TITLE**

**Patient-Titrated Automated Intermittent Boluses of Local Anesthetic vs. a Continuous Infusion *via* a Perineural Catheter for Postoperative Analgesia**

**4. ESTIMATED DURATION OF THE STUDY**

Three years

**5. LAY LANGUAGE SUMMARY OR SYNOPSIS (no more than one paragraph)**

Continuous peripheral nerve blocks (cPNB) provide prolonged pain relief after surgical procedures, allowing for decreased opioid consumption and improved quality of life. There are three general methods—frequently combined—for dosing of local anesthetic in cPNB: continuous infusion, patient administered boluses, and automated intermittent boluses. To date, nearly all trials involving ultrasound-guided catheter insertion have failed to detect analgesic superiority of one administration modality over the other with equivalent hourly local anesthetic volume and dose. However, we recently completed an IRB-approved randomized, controlled trial at UCSD suggesting that automated intermittent boluses may provide a longer duration of treatment—thus prolonging analgesia—for ambulatory patients having painful foot and ankle orthopedic procedures (200247). While the pump would allow patients to administer additional, non-automated boluses to supplement the programmed automated intermittent boluses if they experienced pain, it did not permit patients to decrease the amount of local anesthetic they were receiving. And it appeared that many patients were receiving more local anesthetic than they required.

The FDA-cleared portable infusion pump used in that study (Infutronix, Natick, Massachusetts) now has a new and novel feature which will potentially improve the patient experience: it is now possible for patients to easily self-titrate the volume of local anesthetic administered with each automatic bolus. Using this feature, patients can increase or decrease the amount of local anesthetic they receive and titrate within a physician-specified range to their level of pain.

In the United States, the vast majority of forearm fractures as well as foot and ankle surgery is now performed on an outpatient basis. ***For ambulatory patients who are discharged home with a set local anesthetic reservoir volume, decreasing the rate of anesthetic consumption will allow prolonging the continuous peripheral nerve block and therefore analgesia.*** In other words, even if automated repeated boluses provide equivalent analgesia compared with a continuous peripheral infusion, the automated bolus dose method will be superior if it consumes less local anesthetic thereby permitting a longer analgesic treatment. In the outpatient arena, titratable automated intermittent boluses offer two different opportunities to improve postoperative pain control: (1) improved analgesia in the initial days following surgery; and, (2) improving analgesia by allowing prolonged administration past the time at which a continuous infusion would have exhausted the anesthetic reservoir.

**6. SPECIFIC AIMS**

**Specific Aim:** To determine the relationship between method of local anesthetic administration (continuous with

PCA vs. titratable intermittent dosing with PCA) for continuous peripheral nerve block and the resulting pain control.

**Hypothesis:** We hypothesize that, compared with a traditional ***fixed, continuous basal infusion initiated prior to discharge***, perineural local anesthetic administered with titratable ***automated boluses at a lower dose and a 5-hour delay*** following discharge will (1) provide at least noninferior analgesia during the period that both techniques are functioning; and, (2) will result in a longer overall duration of administration [dual primary end points].

## 7. BACKGROUND AND SIGNIFICANCE

**Continuous peripheral nerve blocks:** In the postoperative setting, pain is a primary concern of patients and healthcare providers. Over 40% of ambulatory patients undergoing orthopedic procedures experience moderate-to-severe postoperative pain at home. A single-injection peripheral nerve block provides up to 15 and 24 hours of analgesia following upper and lower extremity procedures, respectively. However, following this initial period, patients must rely on other, less potent, analgesics such as oral and intravenous opioids. A continuous peripheral nerve block (CPNB)—also called perineural local anesthetic infusion—offers an alternative analgesic option. This technique involves the percutaneous insertion of a catheter directly adjacent to the peripheral nerve(s) that innervate the surgical site at the same time the initial regional block is placed. During the past decade, ultrasound-guided catheter placement has also become the common method for placing perineural catheters. Using this technique, the peripheral nerve(s) is visualized in real-time using ultrasound, and then the catheter is placed directly adjacent to the nerve(s), also under real-time ultrasound guidance.

**Local anesthetic infusion methods:** There are three general methods—frequently combined—for dosing of local anesthetic in CPNB: continuous infusion, patient administered boluses (PCA), and automated intermittent boluses. Automated intermittent boluses with PCA has been shown to be superior to continuous infusion with PCA for patients undergoing painful foot surgeries when the perineural catheter is placed using nerve stimulation for needle placement followed by blind insertion of a non-stimulating perineural catheter. However, in the past decade ultrasound guidance has overwhelmingly become the dominant modality for administering peripheral nerve blocks and inserting perineural catheters. To date, nearly all trials involving ultrasound-guided catheter insertion have failed to detect analgesic superiority of one administration modality over the other with equivalent hourly local anesthetic volume and dose. However, we recently completed an IRB-approved randomized, controlled trial at UCSD suggesting that automated intermittent boluses may provide a longer duration of treatment—thus prolonging analgesia—for ambulatory patients having painful foot and ankle orthopedic procedures (200247). While the pump would allow patients to administer additional, non-automated boluses to supplement the programmed automated intermittent boluses if they experienced pain, it did not permit patients to decrease the amount of local anesthetic they were receiving. And it appeared that many patients were receiving more local anesthetic than they required.

The FDA-cleared portable infusion pump used in that study (Infutronix, Natick, Massachusetts) now has a new and novel feature which will potentially improve the patient experience: it is now possible for patients to easily self-titrate the volume of local anesthetic administered with each automatic bolus. Using this feature, patients can increase or decrease the amount of local anesthetic they receive and titrate within a physician-specified range to their level of pain. The Nimbus pump manufactured by Infutronix has 510(k) clearance for the following indications: “To deliver medications and/or fluids to a patient under the direction or supervision of physician or other certified healthcare professional in clinical or nonclinical environments, such as homes. The device is intended for subcutaneous, percutaneous, perineural, epidural and intravenous infusion, including but not limited to patient controlled analgesia (PCA) delivery.” The following precautions are provided by the manufacturer:

- Only use pump as directed by physician or other certified health care professional.
- The pump is not to be used for delivery of blood or cellular blood products.
- The pump is not intended for delivery of life-sustaining medication.
- Do not use the pump or cassette/administration set to administer any infusion to the epidural space unless the medication and/or fluid infused is indicated for epidural administration.
- If the pump is used to deliver critical medication, a backup pump should be available.
- Do not use the pump in or near an MRI (Magnetic Resonance Imaging) device.

In the United States, the vast majority of forearm fracture as well as foot and ankle surgery is now performed on an outpatient basis. For ambulatory patients who are discharged home with a set local anesthetic reservoir volume, decreasing their hourly consumption of anesthetic will allow prolonging their continuous peripheral nerve block and therefore their analgesia. In other words, even if automated repeated bolus doses provide equivalent analgesia as a continuous peripheral infusion, the automated bolus dose method will be superior if it consumes less local anesthetic, thereby permitting a longer analgesic treatment. In the outpatient arena, titratable automated intermittent boluses offer two different opportunities to improve postoperative pain control: (1) improved analgesia in the initial days following surgery; and, (2) improving analgesia by allowing prolonged administration past the time at which a continuous infusion would have exhausted the anesthetic reservoir.

## 8. PROGRESS REPORT

Not applicable.

## 9. RESEARCH DESIGN AND METHODS

This will be a randomized, controlled investigation.

### Table of Events

Postoperative Day	Experimental?	Event
0	Yes	Written, informed consent
0	No	Anthropometric information collected
0	No	Ultrasound-guided popliteal-sciatic perineural catheter insertion
0	No	Single-injection peripheral nerve block with ropivacaine 0.5%
0	Yes	Randomization
0	No	Ropivacaine 0.2% perineural local anesthetic administration begins
0	Yes	Local anesthetic administered as basal or programmed bolus doses
1-9	Yes	Patients contacted by phone to collect data
5-8	Yes	Perineural catheters removed with reservoir exhaustion or Day 8

**Enrollment:** Consenting adults undergoing ulnar and/or radius fracture open reduction internal fixation or painful foot and/or ankle surgery with a planned infraclavicular or popliteal-sciatic perineural catheter insertion, respectively, will be offered enrollment. Study inclusion will be proposed to eligible patients prior to surgery. If a patient desires study participation, written, informed consent will be obtained using a current UCSD IRB-approved ICF. Selection for inclusion will not be based on gender, race, or socioeconomic status. The study population of interest includes men and women of all races and socioeconomic status. Inclusion and exclusion criteria are listed in section #10 below.

### Preoperative Procedures:

*SOC (mandated for study purposes):* Following written, informed consent, subjects will have baseline anthropometric information (e.g., age, sex, height, weight) collected and a sciatic perineural catheter inserted by a regional anesthesia fellow or resident under the direct supervision and guidance of a regional anesthesia attending (or by the attending him/herself).

*Per standard of care,* all subjects will have an ultrasound-guided infraclavicular or popliteal-sciatic perineural catheter inserted as previously described.

*SOC (mandated for study purposes):* After catheter insertion, ropivacaine 0.5% (20 mL, with epinephrine) will be administered via the catheter under ultrasound visualization. Sensation in the brachial plexus or tibial/peroneal nerve distributions will be checked for anesthetic effect. A “successful” regional block will be defined as sensory- and motor-block onset within the 30 minutes following the local anesthetic injection.

A saphenous nerve block with ropivacaine 0.5% (and epinephrine) may or may not be provided, depending on the surgical procedure, *per standard of care*.

#### **Intraoperative:**

The initial local anesthetic bolus may provide complete surgical anesthesia for the procedure. Patients who desire a general anesthetic or experience a partial block that is not adequate for surgical anesthesia will receive a general anesthetic, *per standard of care*.

#### **Randomization:**

*Experimental:* Subjects will be randomized to one of two treatment groups: (1) **titratable automated intermittent bolus** or (2) **continuous infusion** in a computer generated 1:1 ratio using opaque envelopes opened only after successful catheter insertion is documented within 30 minutes of the local anesthetic injection.

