#### **Postoperative Procedures:**

*SOC (mandated for study purposes):* Following completion of the procedure in the operating room, an infusion pump (Infutronix, Natick, Massachusetts) with a 500 mL ropivacaine 0.2% reservoir will be attached to the perineural catheter. For patients in the **continuous infusion** group, the pump will provide an 8 (infraclavicular) or 6 (sciatic) mL/h basal infusion and a 4 mL patient-controlled bolus with a 30-minute lockout (standard at UCSD).

*Experimental:* For patients in the **titratable automated intermittent bolus** group, the pump will provide an automatic 11 (infraclavicular) or 8 (sciatic) mL bolus once every 2 hours and have a 4 mL patient-controlled bolus with a 30 minute lockout. In addition, for those in the **titratable automated intermittent bolus** group, the infusion pump will be set in a “pause” mode that delays initiation of the automated bolus doses by 5 hours (this can be over-ridden by patients if they would like to initiate their perineural infusion earlier than 5 hours). Lastly, subjects in the **titratable automated intermittent bolus** group will be able to titrate the volume of their automated bolus up or down within the range of 1-16 mL.

*Per standard of care,* the pump will not administer more than 20 mL during each hour (below the current UCSD maximum). Prior to discharge, the functioning of the infusion pump will be explained, so that they understand that they should push the bolus button if they have pain. This is accurate regardless of which treatment group the patient is randomized to, ensuring that all subjects will receive adequate analgesia.

*Experimental:* Subjects will be contacted via phone for the 9 days following surgery to collect information regarding surgical pain (Numeric Rating Scale of 0 to 10, with “0” being no pain and “10” being the worst pain ever experienced), analgesic use, sleep disturbances, infusion side effects, and satisfaction with pain control. When 500 mL has been infused or on Day 8—whichever comes first—subjects will remove the catheter and

place the pump in a pre-addressed and -stamped package for return [note that it is standard of care for patients to remove the catheters at home; but, listed as experimental here due to the timing of catheter removal which will be later than is standard of care due to the experimental local anesthetic administration protocol].

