**Data Acquisition [all experimental]:**

Data will be gathered from the patients' electronic medical record, by telephone follow-up, and from the memory of each infusion pump. Subjects will be contacted by phone for the 9 days following surgery. Data will be recorded on paper Case Report Forms, including: patient name, medical record number, age, sex, height, weight, surgical procedure, date of procedure, anesthesiology attending overseeing/placing catheter, randomization number, whether a femoral/saphenous block was placed, if the catheter was placed per protocol, if the block set up successfully, intraoperative fentanyl, morphine and dilaudid, and the time of infusion initiation.

**Outcomes (End Points):** For the first 9 postoperative days, subjects will be asked to answer the questions with regard to the previous 24 hours: opioid consumption, worst pain, average pain, least pain, current pain (Numeric Rating Scale for all pain scores), any numbness on extremity (scale 0=absent to 10=insensate), fluid leakage (yes/no), number of sleep disturbances due to pain (awakenings), satisfaction with analgesia (0=very dissatisfied, 10=very satisfied), the bolus volume for subjects in the titration group, and the seven questions of the Brief Pain Inventory's Interference Scale. The date and time of infusion completion will be recorded as will the reason for catheter removal (reservoir exhaustion vs. another reason).

**Statistics:** The infraclavicular and popliteal-sciatic groups will be analyzed separately as two distinct analyses. This study will be powered for two primary end points: (1) the average NRS queried on postoperative day 1; and (2) the duration of treatment from when the infusion pump was initially turned on until the local anesthetic reservoir was exhausted [recorded by the infusion pump memory]. The dual hypotheses will be tested with a serial testing strategy, such that Hypothesis 2 will not be formally tested unless the conclusion of Hypothesis 1 is at least "noninferiority". Following the approach described in Althunian et al, noninferiority will be assessed by comparing the lower limit of the 95% confidence interval for the difference (CB minus AB) on the NRS (range: 0 to 10) to a pre-specified noninferiority margin of 1.7 NRS units (see Figure 1). This will provide evidence that the analgesia provided by the novel automated boluses is no worse than 1.7 NRS units compared to CB.

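### The protocol lets the allocation envelope be opened before surgery, although the arms do not differ until the pump is attached afterwards; tie opening to pump programming

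*Combined protocol and SAP*

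**What the plan says.** - **Opening the envelope.** The Randomization section (section 9) specifies 1:1 allocation by "opaque envelopes opened only after successful catheter insertion is documented within 30 minutes of the local anesthetic injection". It sets no latest time and does not say who opens the envelope.
- **When block success is known.** Preoperative Procedures defines it as "sensory- and motor-block onset within the 30 minutes following the local anesthetic injection".
- **When the arms separate.** Postoperative Procedures begins "Following completion of the procedure in the operating room, an infusion pump" is connected. Everything that distinguishes the arms (basal rate or automated boluses, the 5-hour pause, self-titration) is a setting of that pump.
- **Order of events.** In the Table of Events, Randomization comes directly after the single-injection block and directly before the row "Ropivacaine 0.2% perineural local anesthetic administration begins". Surgery has no row.
- **Care that can fall in between.** A saphenous block "may or may not be provided, depending on the surgical procedure". On anesthesia, the Intraoperative section says: "Patients who desire a general anesthetic or experience a partial block that is not adequate for surgical anesthesia will receive a general anesthetic". The case report form records "whether a femoral/saphenous block was placed, if the catheter was placed per protocol, if the block set up successfully, intraoperative fentanyl, morphine and dilaudid", but the protocol gives no rule for intraoperative opioids.
- **Masking and balance.** No masking of patients, clinicians or assessors is described. The baseline balance check names age, sex, height, weight and BMI.

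**The concern.** Nothing in the allocated treatment is needed before the pump is programmed. If the envelope is opened earlier, knowledge of the arm has no use during the operation, but it can influence care that the protocol leaves to judgment. The Informed Consent section says the investigators are the regional anesthesiologists who give routine care, so those who know the arm and those who treat the patient may be the same people.

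At stake is average pain on postoperative day 1. It is recalled over the preceding 24 hours, and duration is formally tested only if noninferiority on it is concluded. More analgesia in the bolus arm would push toward noninferiority; more in the continuous arm would push away from it. Treatments given after allocation are also not clean adjustment covariates, so a later regression would not be a sound repair.

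Opening early can also randomize a patient who never has a pump attached. The Statistics section defines no analysis set that says how such a patient is handled, and treatment duration is measured from when the pump is turned on.

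**Working it through.** **1. Timeline from the text.**

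| Step | Source | Allocation may be known? |
|---|---|---|
| Catheter and initial block | Preoperative Procedures | No, completed first |
| Block success documented within 30 minutes | Preoperative Procedures; Randomization | From here on |
| Saphenous block, sciatic cohort, if given after opening | Preoperative Procedures | Not excluded |
| Anesthetic type and intraoperative opioids | Intraoperative; Data Acquisition | Not excluded |
| Pump attached, arms first differ | Postoperative Procedures | Necessarily |

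The catheter and initial block are protected. The steps between documented success and the pump are not. The 30-minute limit qualifies the documentation of success, not the opening of the envelope.

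**2. Which route applies to which cohort.** The cohorts are analyzed separately. Intraoperative opioids are a route in both. Anesthetic type is a route in both, but only where it is not settled by the patient's wish or an inadequate block. The saphenous block concerns the sciatic cohort only, is tied to the operation, and may precede opening.

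**3. Size.** The plan gives no figure on this point, so there is none to reproduce. It gives no rate of any co-treatment by arm and no effect on pain. What can be shown is how sensitive the day 1 test would be to an assumed shift *b* in mean NRS between the arms.

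Inputs from the plan: 35 per group, margin 1.7, 95% confidence interval, NRS interquartile range about 1 to 4. Assumptions: normal approximation, with one of two SDs.
- From the interquartile range: 3 / (2 × 0.6745) = 2.22.
- The SD that gives about 80% power under equality, close to the plan's simulated 79.2%: 1.7 / [(1.960 + 0.842) × √(2/35)] = 2.54.

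SE = SD × √(2/35), which is 0.532 for SD 2.22 and 0.607 for SD 2.54.

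- Chance of wrongly concluding noninferiority when the true deficit is 1.7 and *b* favors the bolus arm: Φ(b/SE − 1.96).
- Chance of concluding noninferiority under true equality when *b* goes against the bolus arm: Φ((1.7 − b)/SE − 1.96).

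| Assumed shift *b* (NRS) | False noninferiority, SD 2.54 / 2.22 | Noninferiority concluded under equality, SD 2.54 / 2.22 |
|---|---|---|
| 0 | 2.5% / 2.5% | 80% / 89% |
| 0.1 | 3.6% / 3.8% | 75% / 85% |
| 0.2 | 5.2% / 5.7% | 70% / 81% |
| 0.3 | 7.1% / 8.1% | 64% / 75% |
| 0.5 | 12.8% / 15.4% | 51% / 62% |

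The table shows that the test reacts to small shifts in either direction. It does not show which row, if any, applies.

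**4. Room for the change.** Each cohort plans 70 subjects plus 30 for those who cannot be randomized or who withdraw. That is 100 per cohort and 200 in total.

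**The case against.** The strongest reply is that the text does not put opening before surgery. Randomization is printed after Intraoperative and before Postoperative Procedures, and the Table of Events lists it directly before the perineural infusion begins. Both fit an envelope opened near pump attachment. This stands as a reading. It does not settle the matter, because the sentence itself sets only an earliest time.

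The reply continues that the co-treatments leave limited discretion. The saphenous block follows the operation, general anesthesia depends on patient wish or an inadequate block, and opioids are recorded, so an imbalance would be visible. This stands in part. It narrows the route but leaves opioids open, and seeing an imbalance does not remove its effect.

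A reader might also infer three stronger things that the documents do not support:

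- *Allocation is released before the operation.* The plan permits this but does not state it.
- *Clinicians would compensate for the 5-hour pause, so the bias favors the bolus arm.* The Background section credits a single-injection block with up to 15 hours of analgesia (upper extremity) or 24 hours (lower extremity). The pause therefore falls largely within the expected initial block, and patients can override it. The motive is weak and the direction open.
- *The bias is 12% to 24% of the margin.* That needs a saphenous effect of 1 to 2 NRS and a 20-point difference in use: 0.20 × 1 to 2 = 0.2 to 0.4, divided by 1.7. Neither input is in the documents. A 5-point difference gives 0.05 to 0.10, or 3% to 6%, and no difference gives zero.

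**Conclusion.** The concern holds as a gap that the plan permits, not as a bias that has been shown. The protocol does not exclude opening the envelope before surgery, the arms do not differ until after it, and no masking is described. Clinicians could therefore know the arm while choosing intraoperative opioids in both cohorts, anesthetic type where discretionary, and a saphenous block in the sciatic cohort if it follows opening.

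The size and direction of any effect on day 1 NRS cannot be determined from the documents; the sensitivity table rests on assumed shifts and a normal approximation. The conclusion rests on the wording of the Randomization section and on the absence of any masking provision. If envelopes are in practice opened at pump attachment, the amendment only records that practice. It is still worth making, because it closes an avoidable route into the gating endpoint at almost no cost.

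**What to change.** Amend the Randomization section so that the envelope is opened only after surgery, when the pump is about to be programmed and attached. Keep documented block success within 30 minutes as the condition for eligibility. Align the Table of Events by adding a row for surgery before Randomization.

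Report saphenous block, anesthetic type and intraoperative opioids by arm. Under the amended timing they are pre-allocation variables, provided any saphenous block was given before opening; recording its time would confirm this.

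The cost is one sentence and one table row, with no change to procedures, treatment settings or the 35 per group. A few patients with a successful block may not reach randomization, which the 30 extra subjects per catheter cohort already cover. In return, patients who never reach pump attachment are no longer randomized. The change does not address what happens once the pump is attached: patients still report pain, and analgesics are still used, with the arm known.
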